### **3.6. Experimental design**

Participation will require 10 separate visits.

- Visit 1 will consist of the interview, speech/language assessments, and a baseline speech sample (~ 1.5 hours).
- Visit 2 will consist of a second baseline speech sample and behavioral testing (~ 2 hours).
- Visit 3 will consist of a third baseline speech sample, MRI, and the first tDCS session (~2 hours).
- Visits 4, 5, 6 will consist of tDCS sessions (~1 hour each; 3 hours total)
- Visit 7 will consist of the final tDCS session, MRI, and behavioral testing (~3.5 hours)
- Visits 8-9 will consist of the second and third post-testing speech sample (~15 minutes each; 30 minutes total)
- Visit 10 will be 1 month (~4 weeks) after visit 7 and will consist of a final speech sample, MRI, and behavioral testing (~3.5 hours)

Visits 3 through 7 must be completed on consecutive days. Participants will also be sent a short online survey about their experiences with the tDCS procedure about 2 days after each visit; this survey will take no more than 5 minutes to complete. The potential amount of time needed for the entire study will be approximately 15-17 hours.

This project employs a between-subjects, sham-controlled, double-blinded design. Participants will be randomly assigned to either active or sham stimulation conditions. Total study time will be 2 weeks, plus a follow up appointment 4 weeks after training ends. Three speech samples (SS) will be collected during the first 1-2 weeks prior to training to obtain average baseline measures of speech fluency. Speech-language (SL) testing and collection of the first speech sample will be during the first visit. Visit 2 will consist of the second baseline speech measure and baseline measures of behavioral performance on the rhythm judgment tasks. On the third baseline visit, designated as Time 1 for analyses in sections 2 and 3 below, pre-training fMRI scans will be acquired and the first HD-tDCS session will be completed. Visits 4-6 will consist of tDCS sessions only. Visit 7 will consist of the final tDCS session, post-training MRI, and post-training behavioral testing and speech sample. Within the next 1-2 weeks, two speech samples (visits 8, 9) will be collected. Visit 10 will be 4 weeks after visit 7 and will consist of the final speech sample, fMRI, and behavioral testing.

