### 1. Specific Aims

- 1.1. Specific Aim #1: Determine effects of anodal HD-tDCS targeting left pSTG on speech fluency in adults who stutter.** Pre-training measures of stuttering severity (e.g., percent stuttering-like disfluencies, OASES scores) will be compared with those same measures immediately following training, as well as 4 weeks post-training. We hypothesize that when paired with a fluency-inducing speech condition, active stimulation targeting left pSTG will lead to a greater increase in speech fluency compared to behavioral training alone (sham stimulation).
- 1.2. Specific Aim #2: Determine effects of anodal HD-tDCS targeting left pSTG on performance on rhythm judgement tasks.** Pre-training measures of performance (reaction time and accuracy) on finger-tapping tasks and rhythm judgment tasks will be compared with those same measures immediately following training, as well as 4 weeks post-training. We hypothesize that when paired with a fluency-inducing speech condition, active stimulation targeting left pSTG will lead to a greater increase in performance on these tasks compared to behavioral training alone (sham stimulation).
- 1.3. Specific Aim #3: Determine effects of anodal HD-tDCS targeting left pSTG on functional connectivity within BGTC regions during speech production.** Pre-training measures of functional connectivity within BGTC regions will be compared before and immediately following training, as well as 4 weeks post-training. We hypothesize that when paired with intensive training under fluency inducing conditions, active stimulation targeting left pSTG will lead to increased functional connectivity within the BGTC network compared to behavioral training alone (sham stimulation).

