**3.2. Assessment.** Prior to assessment, the study will be explained to participants and an informed consent document signed. The assessment will consist of 3 parts: 1) Interview (review of medical history and history of stuttering), 2) standardized tests, and 3) speech sample collection.

**3.3. Interview.** Participants will be interviewed to obtain information on their medical and general speech history, as well as family history of stuttering, stuttering onset, and development. We will also ask questions about their musical training experience.

**3.4. Standardized assessments.** The standardized tests will provide measures of expressive and receptive language/vocabulary, speech fluency/stuttering severity, and working memory. The assessments may consist of the following:

- The Peabody Picture Vocabulary Test ([PPVT-3; Dunn & Dunn, 1997](#))
- Expressive Vocabulary Test ([EVT-3; Williams, 1997](#))
- Overall Assessment of the Speaker's Experience of Stuttering (Yaruss & Quesal, 2010)
- Operation span (Unsworth, Heitz, Schrock, & Engle, 2005)

**3.5. Speech samples.** Speech samples will consist of a reading task and a conversation between the participant and researcher. The reading and conversation will be audio- and video-taped. Speech samples will be transcribed off-

line and analyzed for disfluencies and any unusual speech-language usage. The severity of stuttering will be based on the reading and conversation speech samples collected. The Stuttering Severity Instrument (SSI-4) ([Riley, 2009](#)), will be used to assess the severity of stuttering during these samples. Two trained speech pathologists or research investigators experienced in disfluency analysis will independently score the SSI form to establish reliability of measurement. To be identified as a person who stutters, the overall SSI score is required to be 20 (corresponding to mild stuttering severity) or greater. Additionally, participants will be asked to rate their speech (e.g., very fluent, disfluent) and stuttering (e.g., mild, severe) within and outside the research setting.

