#### **Secondary Outcome Measure 1 - Changes from baseline on the Overall Assessment of Speakers Experience of Stuttering (OASES)**

The OASES is a standardized assessment of the functional impact of stuttering on a person's life. There are 4 sub-tests: general information about speech, your reactions to stuttering, communication in daily situations, quality of life. Each one has a score from 1 to 5 with regard to impact (1 least, 5 most negative impact). These are combined to give a total impact score between 1 and 5, with 5 representing the highest negative impact on person's life. The change on the total impact score will be used.

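### The visit schedule lists the OASES at none of its 10 visits, although the only secondary outcome and Aim 1 need it after training.

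*Combined protocol and SAP*

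**What the plan says.** Four places in the combined protocol and SAP bear on this.

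- **Section 1.1 (Aim 1)** gives OASES as an example of a severity measure and sets its timing: "OASES scores) will be compared with those same measures immediately following training, as well as 4 weeks post-training".
- **Section 3.10, Secondary Outcome Measure 1**, is headed "Changes from baseline on the Overall Assessment of Speakers Experience of Stuttering (OASES" and defines the variable: "The change on the total impact score will be used". It is the only outcome classed as secondary.
- **Section 3.4** lists OASES in the standardized battery, introduced by "The assessments may consist of the following".
- **Section 3.6** sets out 10 visits twice, as a list and as narrative. On standardized testing the narrative says "Speech-language (SL) testing and collection of the first speech sample will be during the first visit". The list gives Visit 2 a second speech sample and behavioral testing, and the narrative describes the same visit as "Visit 2 will consist of the second baseline speech measure and baseline measures of behavioral performance on the rhythm judgment tasks". The list entry for the last training day is "Visit 7 will consist of the final tDCS session, MRI, and behavioral testing (~3.5 hours"; the narrative has "Visit 7 will consist of the final tDCS session, post-training MRI, and post-training behavioral testing and speech sample". Visits 8 and 9 are speech samples only. Visit 10, 4 weeks after Visit 7, has a speech sample, a scan and behavioral testing. OASES appears in neither version.

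**The concern.** A change score needs a baseline value and at least one later value. The section that tells staff what to do at each visit does not list the questionnaire, before or after training. Anyone working from section 3.6 alone would find no instruction to give OASES at Visit 7 or Visit 10. The score records the participant's state at that time and cannot be collected afterwards. With a target of 24 adults who stutter completing the study (section 4.1), even a few missing scores would weaken the only secondary comparison.

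The outcome text also stops at the change in the score and mentions no adjustment for its starting value. In a trial this small, adjustment may give a tighter comparison using a baseline score that the outcome already requires.

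**Working it through.** **1. The schedule, set beside what the outcomes need**

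| Time point needed | Visit by date | What 3.6 lists | OASES named? |
|---|---|---|---|
| Baseline | 1 | interview, speech and language assessments, speech sample | No; inferable through 3.4 |
| Immediately after training | 7 | stimulation, scan, behavioral testing, speech sample (narrative only) | No; timing inferable from Aim 1 |
| 4 weeks after training | 10 | speech sample, scan, behavioral testing | No; timing inferable from Aim 1 |

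OASES is named at 0 of 10 visits. Of the three primary and secondary outcomes, it alone has no named post-training visit. Scans are named at Visits 7 and 10, and speech samples at Visit 7 (narrative), 8, 9 and 10.

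**2. Possible indirect routes in 3.6**

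- *Behavioral testing.* The narrative for Visit 2 explains it as the rhythm tasks. Section 4.2 uses the term as a general heading, so a broader reading is possible, but no text says it includes OASES.
- *Online survey.* It concerns the stimulation procedure.
- *Stated time.* The listed durations add to 1.5 + 2 + 2 + 3 + 3.5 + 0.5 + 3.5 = 16.0 hours, which agrees with the plan's 15 to 17 hours. No separate OASES time is shown, and the documents do not say how long it takes, so the total settles nothing.

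**3. What baseline adjustment would gain**

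The plan gives no figure to reproduce. Inputs: 24 completers (section 4.1), assumed split 12 and 12; equal variances at baseline and follow-up (assumed); baseline-to-follow-up correlation r (assumed, since the documents give none).

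- Unadjusted change: variance of the group difference, in SD² units, is 2(1 − r) × 2/12, with 22 degrees of freedom.
- Adjusted for baseline: on average (1 − r²) × 2/12 × (1 + 1/20), with 21 degrees of freedom.
- Average variance ratio, adjusted to unadjusted: (1 + r)/2 × 1.05.

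| r | Variance ratio | Reduction | 95% half-width, unadjusted (SD) | 95% half-width, adjusted (SD) |
|---|---|---|---|---|
| 0.5 | 0.788 | 21% | 0.847 | 0.753 |
| 0.7 | 0.893 | 11% | 0.656 | 0.621 |
| 0.9 | 0.998 | 0% | 0.379 | 0.379 |

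Simulated ratios (40,000 runs each) were 0.788, 0.896 and 1.002. The ratio reaches 1 at r = 2/1.05 − 1 = 0.905.

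**4. What adjustment can cost**

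The factor 1.05 is an average over random allocations. In a given trial it is 1 + t²/22, where t is the t statistic for the chance baseline difference between arms. It exceeds 1.05 in about 31% of allocations and about 1.195 in 5% of them.

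Unequal variances also matter. If the post-training SD is k times the baseline SD, the ratio is k²(1 − r²) × 1.05 / (1 + k² − 2rk). At r = 0.7:

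- k = 0.8: 0.64 × 0.51 × 1.05 / 0.52 = 0.66
- k = 1.2: 1.44 × 0.51 × 1.05 / 0.76 = 1.01

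**The case against.** The best reply is that the protocol, read as a whole, does give the timing. Aim 1 sets the OASES comparisons, Visit 7 is the last training day, and Visit 10 is 4 weeks later. No text says that OASES is given only once. Section 3.6 is plainly not exhaustive: its Visit 7 entry omits the speech sample that the narrative includes, and the side-effects questionnaire in section 4.2 is not in the schedule at all. Absence from the list is therefore weak evidence that a measure is unplanned.

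Most of that stands, and it rules out three stronger readings.

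- A reader might infer that the protocol contradicts itself. It does not; the schedule is incomplete.
- A reader might infer that OASES would not be collected after training, so that the secondary outcome could not be computed. The documents do not show this. Staff who follow Aim 1 and section 3.10 could collect it at Visits 7 and 10.
- A reader might infer that OASES is the only one of the six outcomes in 3.10 without a route to a post-training value. That would be uneven. The 1-to-9 self-rating of fluency is not named at any visit either, and its route through section 3.5 is thin. Only the comparison with the two primary outcomes holds.

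It is also fair to say that the precision argument is separate from the missing entry: adjustment would not cure an uncollected score. Nor does section 3.10 rule adjustment out, since it names a variable and not a model.

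What remains is that no visit instruction contains the questionnaire, and the only list that does is worded as optional.

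**Conclusion.** The point holds as an incomplete schedule of minor to moderate weight. The sole secondary outcome depends on a questionnaire listed at none of the 10 visits. Its baseline rests on an optional battery, and its later time points have to be pieced together from the aims. Neither primary outcome is affected. The risk is avoidable missing data that cannot be recovered.

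The precision gain is a secondary reason to act and rests on assumptions: 12 per arm, equal variances and an unknown correlation. On those terms adjustment helps at moderate correlations, is neutral near 0.9, and loses on average only above that. It can also lose slightly if the post-training SD is well above baseline. The 5% cost should not be read as a ceiling, because it is an average that a large chance imbalance would exceed.

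**What to change.** 1. In section 3.4, make OASES required for adults who stutter. In section 3.6, list it at Visits 1, 7 and 10, in both the list and the narrative, to match Aim 1.
2. In section 3.10, Secondary Outcome Measure 1, state that the groups are compared on the OASES total impact score adjusted for the Visit 1 score. Either the change or the post-training score may be the response, since with that adjustment both give the same treatment estimate.

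The first change costs protocol wording and some participant time at visits that already take place. The second costs one degree of freedom (22 to 21) and, on average, about 5% in variance before the gain is counted, more if the arms differ widely at baseline by chance. If the sponsor prefers unadjusted change, the first change is still needed.

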### **3.7. Rhythm judgment and tapping tasks**

Participants will complete tests of rhythm perception and judgment, including finger tapping and beat similarity judgments. These tasks will be completed on a computer or iPad and will take between approximately 2 hours to complete. Participants will be seated in a comfortable chair in a quiet room during testing.

### **3.8. HD-tDCS protocol**

**Stimulation parameters and target location.** Stimulation will be delivered using a Soterix 4x1 HD-tDCS adapter with the 1x1 tDCS for Clinical Trials system. Modeling software (HD-Explore™, Soterix Medical Inc.) will be used to determine the best electrode montage to optimize targeting of left pSTG. The 4 (cathode) x 1 (anode) montage produces reliable changes in the electric field, and limits the stimulation area to within the area

circumscribed by the montage. A current of 2mA was selected because it is well-tolerated, safe, and effective (Bikson et al., 2016; Woods et al., 2016).

**Procedure and tasks.** During each session of the training period, stimulation (active or sham) will be delivered 20 minutes daily for 5 consecutive days. In both active and sham conditions current is automatically ramped up over 30 seconds. In the sham condition current is ramped down to zero for the remainder of the time to avoid stimulation of the brain. During stimulation, participants will engage in choral speech by reading overtly with a recording of the same text at a comfortable rate. Text will be at a 5th grade level and sufficient in length such that repetition of text will not occur during training.

### **3.9. fMRI protocol**

**Procedure.** All participants will be scanned to assess brain activation within the speech motor control network. Procedures will be identical and scan time will be about 1 hour at each time point. All fMRI scans will be acquired at the University of Michigan fMRI laboratory using a 3T GE MRI scanner (MR 750). A standard echoplanar pulse sequence will be used. High-resolution structural images will be acquired at the beginning of each session using spoiled gradient-recalled acquisition in steady state (SPGR) imaging. Recent advancements in de-noising methods by [name] and colleagues (Xu et al., 2014) allow us to collect fMRI data during continuous, narrative speech providing a more natural speaking condition than is typically used in task-based fMRI studies. Speech in the scanner will be recorded with an optical noise cancellation microphone and an MR-compatible camera mounted on the scanner head-coil. Resting state fMRI will also be acquired.

**Stimuli and tasks.** During the functional scanning, participants will complete continuous speech production tasks.

### **3.10. Data analysis**

#### **Primary Outcome Measure 1- Changes in brain activation as assessed by fMRI images**

Functional images will be de-noised using spatial Independent Component Analysis (sICA), a signal un-mixing algorithm to separate speech and movement artifacts (Xu et al., 2014). This method has been validated against PET studies (Xu et al., 2014) and used to study continuous speech production (AbdulSabur et al., 2014). Task-based and functional connectivity analysis will be conducted using the conditions which contained continuous speech. We expect the magnitude of change to be greater in the active group than in training alone (sham tDCS). The functional connectivity analyses will be conducted on both task-based and resting state data.

#### **Primary Outcome Measure 2 - Change in percentage of stuttered syllables produced during speech sample (speech fluency)**

To measure effects of tDCS on fluency we will calculate %SLD at each of the 3 time points. Two speech pathologists trained in disfluency analysis and blinded to group assignment and time point will independently score %SLD to establish reliability. The outcome measure is the difference between baseline measures of (mean) %SLD and the same measure at 2 post-training time points. While an increase is expected to occur in both groups, we expect that the magnitude of any differences will be greater in the group receiving active stimulation compared to training alone (sham stimulation). We expect that: 1) %SLD will decrease significantly more in the active stimulation group compared to the sham group, and 2) these differences will be maintained when assessed 4 weeks later.

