### 3. Method

#### 3.1. Subject Recruitment and Screening

Participants will be recruited through community advertisements such as UMHSClinicalStudies.org or Craigslist, in the hospital, community, local papers; word of mouth; letters to area clinicians; stuttering support groups; through the National Stuttering Association website; and on lab websites and Facebook pages ([www.neurostutteringresearch.com](http://www.neurostutteringresearch.com), [www.facebook.com/msudevelopmentalstutteringproject/](http://www.facebook.com/msudevelopmentalstutteringproject/)). We also will post infrequently in other relevant Facebook groups. All potential participants who contact the study coordinator will be briefed on the study and screened to ensure eligibility criteria are met. If the criteria are met, a face-to-face interview will be arranged, during which the written consent form will be completed, and the full assessment will occur. Information about the study may also be exchanged via email but participants will be discouraged from communication any personal information via the email system. Participants will be contacted up to 3 times if no response is received following their initial contact with the research team.

**General participant criteria.** The following criteria must be met by all participants:

- Between the ages of 18 and 65 years
- A history of persistent developmental stuttering,
- Stuttering severity ranging from mild to very severe, specifically Stuttering Severity Instrument (SSI) total score of 20 or higher and/or stuttering rates of 3% or higher,
- Not received any treatment for stuttering within the past year,
- No other neurological conditions such as Tourette's syndrome or post-traumatic stress disorder,
- Not taking any medications/drugs that affect brain function.
- No history of serious medical or neurological illness such as epilepsy and Parkinson's disease,
- No history of closed head injury (e.g., concussion),
- No history of reading disorders,
- No hearing loss,
- Not taking any medication, prescription or non-prescription with any psychotropic effects at the time of the study,
- No metal or electronic implants such as cochlear implants, and pacemakers,
- Scores within 1SD of the norm on the standardized tests for the study.

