## **4. Protection of Human Subjects**

### **4.1. Risks to Human Subjects**

#### **Human Subjects Involvement, Characteristics, and Design**

The proposed study will involve healthy adult participants between 18-65 years of age. All participants in the tDCS arm will be those who have been diagnosed with developmental stuttering. Although women are underrepresented in samples of adults with stuttering, we will make every effort to include women in the proportion they occur in the population with this disorder. While the ratio is closer in childhood, approximately 3 males to 1 female, in adults the ratio is approximately 5 males to 1 female. We will gather information on each participant's medical, social, and developmental history, and speech, language, and hearing background. In addition, stuttering participants will be audio-video recorded to obtain speech samples during conversation and reading. These will be used to determine their stuttering severity level using the standardized assessment, stuttering severity instrument (SSI-4; Riley 2009). Two trained speech-language pathologists experienced in disfluency analysis will independently score the SSI form to establish reliability of measurement. Participants will be randomly assigned to one of the two groups (active vs. sham stimulation).

In order to reach our target of 24 eligible adults who stutter who complete the study, and 50 eligible controls to participate in the rhythm tasks sub study only (see section 4.5 below), we will consent up to 200 people during the oral phone screening. It is possible that some participants who pass this screening may still become ineligible during the first visit, for example due to scoring below normal on the standardized tests, or having a stuttering score that is too low.

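### The primary fluency outcome and OASES are defined as change from baseline, with no baseline covariate pre-specified, in 24 completers whose stuttering runs from mild to very severe

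*Combined protocol and SAP*

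**What the plan says.** All references are to the combined protocol and SAP.

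- **Fluency outcome** (section 3.10, Primary Outcome Measure 2): "The outcome measure is the difference between baseline measures of (mean) %SLD and the same measure at 2 post-training time points". The stated expectation is that "SLD will decrease significantly more in the active stimulation group compared to the sham group", and that the difference persists 4 weeks later.
- **OASES** (section 3.10, Secondary Outcome Measure 1): "The change on the total impact score will be used".
- **Baseline data** (section 3.6): "Three speech samples (SS) will be collected during the first 1-2 weeks prior to training to obtain average baseline measures of speech fluency".
- **Follow-up** (section 3.6): "Visit 10 will be 4 weeks after visit 7 and will consist of the final speech sample". The 4-week value therefore rests on one sample.
- **Allocation** (section 3.6): "Participants will be randomly assigned to either active or sham stimulation conditions". Section 4.1 says no more than this. No ratio, blocking, stratification or minimisation is given.
- **Population** (section 3.1): "Stuttering severity ranging from mild to very severe".
- **Size** (section 4.1): "In order to reach our target of 24 eligible adults who stutter who complete the study".

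For these two outcomes, section 3.10 names no test, model, covariate or significance level for the comparison between arms.

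**The concern.** A comparison of raw change between arms fixes the slope of the post-training value on the baseline value at 1. The true slope is below 1 if single sessions are noisy, or if people with more severe stuttering improve by more in absolute terms. Any chance difference in baseline severity between the arms then carries into the treatment estimate. With two small arms and a wide severity range, a noticeable difference is likely enough to plan for.

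Three things are at stake:

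- **Conditional error.** The unadjusted estimate is unbiased over repeated randomisations, but not given the imbalance that actually occurs.
- **Precision.** The unadjusted comparison may have the larger variance.
- **Choice after the data.** Because the wording fits either analysis, the more favourable one could be reported. That raises type I error even where adjustment would bring no precision.

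**Working it through.** **Inputs.** From the documents: 24 completers, two arms, baseline as the mean of three samples, and one sample at 4 weeks. The documents give no SD, correlation, effect size, alpha, power or allocation ratio, so the 24 cannot be reproduced and the rest is assumed. Assumptions: 12 per arm, two-sided 5%, baseline-to-post correlation rho, and post SD = k × baseline SD. The slope of post on baseline is then k × rho.

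**Step 1. Post value or change as outcome.** Change is the post value minus baseline. Regressing either on arm plus baseline gives the same arm coefficient; only the baseline slope differs, by 1. The two estimates agreed to within 1e-14 in simulation. Defining the outcome as change therefore does not settle whether the analysis is adjusted.

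**Step 2. Size of the imbalance.** SD of the difference in baseline means = sqrt(1/12 + 1/12) = 0.41 baseline SD. P(|difference| > 0.5 SD) = 22%. With an 8:16 split, sqrt(1/8 + 1/16) = 0.43 and the probability is 25%.

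**Step 3. Effect on the unadjusted estimate.** For an imbalance of one SD of its own distribution (0.41 baseline SD), the shift in standard errors of the unadjusted estimate is |1 − k·rho| / sqrt(1 + k² − 2k·rho). At k = 1 and rho = 0.5 this is 0.5/1 = 0.50. At rho 0.7, 0.8 and 0.9 it is 0.39, 0.32 and 0.22.

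**Step 4. Variance and power.** The variance ratio, adjusted over unadjusted, is k²(1 − rho²) / (1 + k² − 2k·rho), times 1 + 1/(24 − 4) = 1.05 for estimating the slope. At k = 1 and rho = 0.5: 0.75/1.00 × 1.05 = 0.79. The last column is adjusted power where unadjusted power is 60%.

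| k | rho | Variance ratio | Adjusted power |
|---|---|---|---|
| 1 | 0.5 | 0.79 | 70% |
| 1 | 0.7 | 0.89 | 65% |
| 1 | 0.9 | 1.00 | 60% |
| 1 | 0.95 | 1.02 | 59% |
| 1.1 | 0.9 | 1.05 | 58% |

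At k = 0.8 the ratio is 0.60 to 0.67 for rho 0.5 to 0.9. Simulation with 40,000 replicates agreed (for example 0.784, 0.893 and 0.998 at k = 1 and rho 0.5, 0.7 and 0.9).

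**Step 5. The plan's own sampling scheme.** Set the between-person variance to 1 and the session-noise variance to q (0.1 to 1), and multiply true severity by s after training. Baseline variance is 1 + q/3, post variance is s² + q/m and the covariance is s. Here m = 3 if the post-training value is the mean of Visits 7-9 (an assumption) and m = 1 at Visit 10. Example with s = 0.9, q = 0.5, m = 1: baseline variance 1.167 and post variance 1.31. The ratio is 1.05 × (1.31 − 0.81/1.167) / (1.31 + 1.167 − 1.8) = 0.955.

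| Shrinkage of true severity | Ratio, post-training | Ratio, week 4 |
|---|---|---|
| None | 0.92–1.03 | 0.98–1.04 |
| 10% | 0.81–0.87 | 0.92–0.96 |
| 20% | 0.53–0.73 | 0.73–0.89 |

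**Step 6. Leaving the choice open.** If whichever analysis is significant is reported, simulated type I error (200,000 replicates per case, k = 1) is 7.4%, 6.9% and 6.3% at rho 0.5, 0.7 and 0.9. Over all cases examined it is 5.8% to 8.0%.

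**Step 7. Skewed data.** With lognormal severity (log SD 0.7) and multiplicative session noise (log SD 0.2 to 0.6), type I error was 4.1% to 4.7% adjusted and 3.9% to 4.3% unadjusted. Neither is inflated.

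**The case against.** The strongest reply is that the plan commits to no analysis at all, so Steps 3 to 5 price a comparison it never selected; the real gap is the missing model. That is partly right. Baseline adjustment is one clause of specifying the model, but it is a clause with a clear answer, and nothing elsewhere in the documents supplies it.

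Second, the precision gain depends on unseen quantities. With the three-sample baseline and no shrinkage of true severity, adjustment is close to neutral and sometimes slightly worse. The large gains need improvement in proportion to severity; section 3.10 expects improvement in both arms but does not say it is proportional. This stands, and it is why the benefit is given as a range.

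Third, the shifts in Step 3 are for a one-SD imbalance, which is exceeded in only 32% of randomisations. At the median absolute imbalance (0.67 of that SD) they are about 0.34, 0.26, 0.21 and 0.15 standard errors. This also stands.

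Fourth, the type I argument supports any pre-specified analysis, and fixing the unadjusted comparison would cure it equally well. That is true, but of the two, adjustment also removes the conditional error, at little cost.

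Finally, no figure here is specific to OASES. The case there is by analogy, although section 3.6 describes averaging of baseline samples only for speech fluency, so the noise-reduction argument does not reach OASES.

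**Conclusion.** The concern holds. Both outcomes are defined as change, no baseline covariate is named, and no stratification by severity is stated. The omission is certain; the size of the benefit is not. Assuming 12 per arm and the ranges of rho, k, session noise and shrinkage above, the adjusted variance runs from 0.53 to 1.05 of the unadjusted variance. Where unadjusted power is 60%, adjustment at k = 1 gives 70% at rho 0.5 and 60% at rho 0.9, and the worst case examined gives 58%. An open choice between the two analyses puts type I error at 5.8% to 8.0%. This should be corrected, with medium confidence in how much it will matter. It does not make the unadjusted estimate biased over randomisations, and the unadjusted test alone is not inflated.

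**What to change.** In section 3.10, pre-specify the primary fluency effect as the active-versus-sham difference in %SLD at the post-training and 4-week time points, with mean baseline %SLD (Visits 1-3) as covariate. State that the treatment estimate is the same whether the post value or the change is the outcome, so the change definition can stay. Say which samples form the post-training value: the visit list in section 3.6 shows no speech sample at Visit 7, while the text below it does. Adjust the OASES total impact score for baseline OASES in the same way. Continue to report raw change by arm descriptively.

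The cost is wording only, since the baseline is already collected. It uses one degree of freedom. Where the slope is near 1, variance rises by about 2% to 5% in the cases examined, or about 2 points of power from 60%. Choosing a primary time point or a multiplicity rule is a separate matter that this change does not settle.
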